### **6.7.1 Handling of study treatment and additional treatment**

#### **6.7.1.1 Handling of study treatment**

Study treatment (inclisiran) must be received by a designated person at the study site, handled and stored safely and properly and kept in a secured location to which only the investigator and designated site personnel have access. Upon receipt, all study treatment must be stored according to the instructions specified on the study medication label. No study medications will be provided for usual care group.

Clinical supplies are to be dispensed only in accordance with the protocol. Technical complaints are to be reported to the respective Novartis CO Quality Assurance.

Medication labels will include storage conditions for the study treatment but no information about the participant except for the medication number.

The investigator must maintain an accurate record of the shipment and dispensing of study treatment in a drug accountability log. Monitoring of drug accountability will be performed by monitors during site visits or remotely and at the completion of the trial.

At the conclusion of the study, and as appropriate during the course of the study, the investigator will return all unused study treatment, packaging, drug labels, and a copy of the completed drug accountability log to the Novartis monitor or to the Novartis address provided in the investigator folder at each site.

## 6.7.2 Instruction for prescribing and taking study treatment

### Packaging and Labeling

Investigational product [inclisiran (KJX839), 284 mg liquid in PFS, 1.5M ml] will be provided by the sponsor. Medication labels will comply with regulatory requirements. The storage conditions will be described on the medication label.

The container closure system for the prefilled syringe consists of a Type I glass syringe with a stainless steel 27G 1/2" staked needle covered by a removable rigid needle shield and Flurotech covered bromobutyl plunger.

**Table 6-4 Dose and treatment schedule**

Investigational / Control Drug (Name and Strength)	Dose	Frequency and/or Regimen
Inclisiran (KJX839), 284 mg liquid in PFS, 1.5 ml	Inclisiran sodium 300 mg/1.5 ml (equivalent to 284 mg inclisiran), s.c. use	Initially, 90 days later, 180 days after the second dose

Participants will be administered a single s.c. injection of 300 mg inclisiran sodium for injection at predefined time points as described in the Schedule of Assessments (Table 8-1). Investigational product injection will be administered by qualified clinical study site staff under the supervision of the investigator or designee. The site of injection is the abdomen, arm or thigh. Do not inject into areas of active skin disease or injury such as sunburns, skin rashes, inflammation, tattoos or skin infections.

All kits of study treatment assigned by the IRT will be recorded in the IRT system.

## 7 Informed consent procedures

Eligible participants may only be included in the study after providing (witnessed, where required by law or regulation), IRB/IEC-approved informed consent.

If applicable, in cases where the participant's representative(s) gives consent (if allowed according to local requirements), the participant must be informed about the study to the extent possible given his/her understanding. If the participant is capable of doing so, he/she must indicate agreement by personally signing and dating the written informed consent document.

Informed consent must be obtained before conducting any study-specific procedures (e.g. all of the procedures described in the protocol). The process of obtaining informed consent must be documented in the participant source documents.

Novartis will provide to investigators in a separate document a proposed informed consent form that complies with the ICH GCP guidelines and regulatory requirements and is considered appropriate for this study. Any changes to the proposed consent form suggested by the investigator must be agreed by Novartis before submission to the IRB/IEC.

Information about common side effects already known about the investigational drug can be found in the Investigator's Brochure (IB). This information will be included in the participant informed consent and should be discussed with the participant during the study as needed. Any new information regarding the safety profile of the investigational drug that is identified between IB updates will be communicated as appropriate, for example, via an investigator notification or an aggregate safety finding. New information might require an update to the informed consent and then must be discussed with the participant.

The following informed consents are included in this study:

- Main study consent, which also included:
  - A subsection that requires a separate signature for the ‘Optional Consent for Additional Research’ to allow future research on data/samples collected during this study
  - As applicable, the consent will include language for the use of de-identification and tokenization technology that will allow for the acquisition and linkage of the participant to their health care data that exists in pharmacy and medical administrative claims databases
- As applicable, Pregnancy Outcomes Reporting Consent for female participants who took study treatment

Women of childbearing potential must be informed that taking the study treatment may involve unknown risks to the fetus if pregnancy were to occur during the study and agree that in order to participate in the study they must adhere to the contraception requirements.

A copy of the approved version of all consent forms must be provided to Novartis after IRB/IEC approval.

Participants might be asked to complete an optional questionnaire to provide feedback on their clinical trial experience.

## 8 Visit schedule and assessments

The Assessment Schedule ([Table 8-1](#)) lists the assessments when they are performed. All data obtained from these assessments must be supported in the participant’s source documentation.

Participants should be seen for all visits/assessments as outlined in the assessment schedule ([Table 8-1](#)) or as close to the designated day/time as possible (+/- 7 days). Missed or rescheduled visits should not lead to automatic discontinuation. Participants may be seen at

any time for an unscheduled visit, e.g., if they experience deterioration or AEs that in the opinion of the Investigator/qualified site staff requires closer monitoring.

Participants who discontinue from study treatment should continue to attend the remaining study visits as indicated in the Assessment Schedule ([Table 8-1](#)).

Participants who discontinue from study or withdraw their consent should be scheduled for a final evaluation visit if they agree, as soon as possible, at which time all of the assessments listed for the final visit will be performed. At this final visit, all investigational product should be reconciled, and the adverse event and concomitant medications not previously reported must be recorded on the eCRF.

Participants will have to comply with the following restrictions during the study:

- Participants need to fast for at least 8 hours for all visits (measurement of lipids/lipoproteins and blood glucose requires participants to be fasting). If the participant has not fasted, the collection of laboratory evaluations must be rescheduled.
- Blood donation will not be allowed at any time during the study

The “X” in the table denotes the assessments to be recorded in the clinical database or received electronically from a vendor. The “S” in the table denotes the assessments that are only in the participant’s source documentation and do not need to be recorded in the clinical database.

As per [Section 4.6](#), during a Public Health Emergency that limits or prevents on-site study visits, alternative methods of providing continuing care may be implemented by the Investigator as the situation dictates. If allowable by a local Health Authority and depending on operational capabilities, phone calls, virtual contacts (e.g. tele consult) or visits by site staff/ home nursing staff to the participant’s home, can replace on-site study visits, for the duration of the disruption until it is safe for the participant to visit the site again.

Table 8-1 Assessment Schedule

Epoch	Screening		Treatment 				
	Visit Name	Visit 1	Baseline/Visit 2	Visit 3	Visit 4	Visit 5	EOS/Visit 6
	Days	-30 to -1	0	90	180	270	330
Inclusion / Exclusion Criteria		X	X				
Informed Consent		X					
Medical History		X					
ASCVD Medical History		X					
Statin Intolerance Medical History		X					
Demography		X					
Pregnancy and Assessments of Fertility 		X	X	X	X	X	X
Height and Weight 		X	X	X	X	X	X
Vital Signs		X	X	X	X	X	X
Physical Examination 		S		S	S	S	S
Electrocardiogram (ECG)		X					
Full Clinical Chemistry			X				X
Limited Clinical Chemistry		X		X	X	X	
Hepatitis Markers		X					
Hematology		X	X		X		X
Coagulation		X	X				X
Urinalysis			X				X
Lipids and Lipoproteins 		X	X	X	X	X	X
Randomization			X				
IRT Transaction		X	X	X	X	X	X
Inclisiran Dose Administration			X	X		X	

Epoch	Screening	Treatment 				
Visit Name	Visit 1	Baseline/Visit 2	Visit 3	Visit 4	Visit 5	EOS/Visit 6
Days	-30 to -1	0	90	180	270	330
Adverse Events	X	X	X	X	X	X
Injection Site Reaction Assessment		X	X	X	X	X
Prior/Concomitant Medications 	X	X	X	X	X	X
Surgical/Medical Procedures	X	X	X	X	X	X
HealthiVibe Trial Feedback Questionnaire 		X		X		X

X Assessment to be recorded in the clinical database or received electronically from a vendor

S Assessment to be recorded in the source documentation only

 Due to a Public Health Emergency, if participant is unable to attend in-person visit, phone or virtual visit is an acceptable alternative. At home visits by site staff or a nursing service may be used to assist with blood draws and/or study medication administration if required at this visit.

 All female participants of childbearing potential will have a serum pregnancy test (hCG) performed at Visit 1 (central lab). A urine pregnancy test will be conducted in the local laboratory for remaining visits.

 Height only to be performed at Visits 1 and 2

 Visits 3, 4 and 5 will be a limited/focused physical examination.

 LDL-C, apolipoprotein B, Lp(a), non-HDL-C, VLDL-C, total cholesterol, triglycerides, and HDL-C. [REDACTED]

[REDACTED]

 30 days prior to randomization

[REDACTED]

 Questionnaire is optional for trial participants.

## 8.1 Screening

A participant who enters screening but is determined not to be eligible will be considered a screen failure. It is permissible to re-screen a participant if he/she fails the initial screening; however, each case must be discussed and agreed with the Sponsor on a case-by-case basis. If the re-screen is approved, a new participant number will be allocated to the participant and he/she will need to re-perform all Visit 1 procedures. A participant may be re-screened once. Participants must provide new written informed consent before they are re-screened.

### 8.1.1 Information to be collected on screening failures

Participants who sign an informed consent form and subsequently found to be ineligible prior to randomization will be considered a screen failure. The reason for screen failure should be recorded on the appropriate Case Report Form. The demographic information, informed consent, and Inclusion/Exclusion pages must also be completed for screen failure participants. No other data will be entered into the clinical database for participants who are screen failures, unless the participant experienced a serious adverse event during the screening phase (see SAE section for reporting details). The IRT must be notified within 2 days of the screen fail.

Participants who are randomized and fail to start treatment, e.g. participants randomized in error, will be considered an early terminator. The reason for early termination should be recorded on the appropriate Case Report Form.

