## **9 Study discontinuation and completion**

### **9.1 Discontinuation and completion**

#### **9.1.1 Study treatment discontinuation and study discontinuation**

Discontinuation of study treatment for a participant occurs when study treatment is stopped earlier than the protocol planned duration and can be initiated by either the participant or the investigator.

The investigator must discontinue study treatment for a given participant if, he/she believes that continuation would negatively impact the participant's well-being.

Study treatment must be discontinued under the following circumstances:

- Participant/guardian decision
- Pregnancy
- Use of prohibited treatment as per recommendations in the prohibited treatment section
- Any situation in which study participation might result in a safety risk to the participant
- Any severe suspected drug related AE at the investigator's discretion

If discontinuation of study treatment occurs, the investigator should make a reasonable effort to understand the primary reason for the participant's premature discontinuation of study treatment and record this information.

Participants who discontinue study treatment or who decide they do not wish to participate in the study further should NOT be considered withdrawn from the study UNLESS they withdraw their consent (see 'Withdrawal of Informed Consent' section). **Where possible, they should return for the assessments indicated** in the Assessment Schedule. If they fail to return for these assessments for unknown reasons, every effort (e.g. telephone, e-mail, letter) should be made to contact the participant/pre-designated contact as specified in the lost to follow-up section. This contact should preferably be done according to the study visit schedule. Unless a participant withdraws informed consent, personal and coded data are able to be collected in accordance with the informed consent form.

If the participant cannot or is unwilling to attend any visit(s), the site staff should maintain regular telephone contact with the participant, or with a person pre-designated by the participant. This telephone contact should preferably be done according to the study visit schedule.

After study treatment discontinuation, at a minimum, in abbreviated visits, the following data should be collected at clinic visits or via telephone/email contact:

- New / concomitant treatments
- Adverse Events / Serious Adverse Events

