### **12.1 Analysis sets**

The Full Analysis Set (FAS) comprises all randomized participants. According to the intent-to-treat principle, participants will be analyzed according to the treatment group they have been assigned to during the randomization procedure.

The Per-Protocol Set is a subset of the Full Analysis Set in which participants are not treated with any inclisiran if they are randomized to the usual care treatment group or do not have any major protocol deviations (including deviations from inclusion/exclusion criteria) in either treatment group.

The Restricted Set 1 is a subset of the Full Analysis Set, which includes only participants without changes in background lipid-lowering therapy.

The Restricted Set 2 is a subset of the Full Analysis Set, which includes only participants who received three doses of inclisiran in the “inclisiran first” implementation strategy group (i.e., excludes patients in the “inclisiran first” implementation strategy group who missed one or more doses) and all participants in the usual care group (including participants who may have used commercially available inclisiran).

The Safety Set includes all participants who received study treatment. Participants will be analyzed according to the study treatment received at randomization.

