2.1.1 General definitions

Study Treatment

The following are the investigational treatments:

- Inclisiran (KJX839), 284 mg, 1.5 ml liquid in a single-use prefilled syringe (PFS) for s.c. administration plus usual care
- Usual care alone

The following treatment labels will be used for all tables, listings and figures:

- Inclisiran First
- Usual Care

Study treatment start and end date

Study treatment start date is defined as the first date when a non-zero dose of study drug is administered for the inclisiran group. If a participant, who is randomized to the Inclisiran First group, does not take any study drug then treatment start date will be the randomization date.

For the usual care alone group the study treatment start date will be the randomization date.

“Day 1” will be used to identify study treatment start date for both treatments.

Study treatment end date is defined as the treatment phase completion date recorded on the “Treatment Disposition” CRF for inclisiran participants. For the usual care alone group, the study treatment end date is the last recorded contact/participation date in the database.

Study start and end date

Study start date is defined as the first date when a non-zero dose of study drug is administered for the inclisiran group. If a participant, who is randomized to the Inclisiran First group, does not take any study drug then study start date will be the randomization date.

For the usual care alone group the study start date will be the randomization date.

Study end date is defined as the date of last recorded contact/participation date in the database.

Planned and actual treatment definitions

Table 2-1 Planned and Actual Treatment Definitions

Randomized Treatment Group	Inclisiran Use Scenario During Study (Inclisiran Use Recorded as Study Treatment or Concomitant Medication)	Planned Treatment	Actual Treatment
Inclisiran First	Received at least one dose of inclisiran	Inclisiran First	Inclisiran First
Inclisiran First	Never received inclisiran	Inclisiran First	Usual Care
Usual Care	Received at least one dose of inclisiran	Usual Care	Inclisiran First
Usual Care	Never received inclisiran	Usual Care	Usual Care

Study day

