Study day will be calculated as (event date – study treatment start date + 1 day) for events that occurred on or after study treatment start date (e.g., visit, lab samples, AEs). For events prior to study treatment start date (e.g., time of diagnosis), study day will be negative and calculated as (event date – study treatment start date). Note that study treatment start date is study Day 1 and the day before study treatment start date is study Day -1 (i.e., no study Day 0).

Baseline and post-baseline definitions

In general, a baseline value refers to the last measurement available prior to administration of the first dose of study treatment (before or on study Day 1). A post-baseline value refers to a measurement taken after the first dose of study treatment (after study Day 1).

Lost to follow up

Participants whose study completion status is unclear because they fail to appear for study visits without stating an intention to withdraw.

On-treatment period

The period where the participants are exposed to the study treatment or usual care. For this study the planned treatment phase consists of 330 days.

Study Completer

Completers are defined as a participant who has a Subject Status of ‘completed’ on the Study Completion/Exit CRF page.

Analysis Visit Windows

The following analysis windows will be used for efficacy and safety analyses.

Table 2-2 Analysis Visit for Each Scheduled Visit

Analysis Visit	Target Study Day*	Analysis Window	
		From	To
Baseline	1		Before randomization/First Study Treatment
Day 90	91	1	135
Day 180	181	136	225
Day 270	271	226	300
Day 330	331	301	375

* Study Day 1 is being used to identify study treatment start date. When calculating study day, the target study day will correspond to the planned study day of the nominal visit. The analysis visit values (Baseline, Day 90, Day 180, Day 270, and Day 330) will be used for all presentations.

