2.5.1 Primary endpoint(s)

The primary efficacy variables are the following:

1. Percent change from baseline in LDL-C
2. Discontinuation of statin therapy (i.e., no statin use \geq 30 days before the end-of-study visit) (yes, no)

The primary analysis time point for both primary efficacy variables is at Day 330.

The following provides additional details on the derivation of primary efficacy variable 2.

If a participant is considered a study completer and has a non-missing visit date for the nominal Day 330 visit recorded, a statin assessment date (to assess if the participant was taking statins at this point in time) will be calculated by subtracting 30 days from the Day 330 visit date (e.g., study Day 300 if the participant completes on study Day 330). The statin assessment date will be compared to the maximum statin end date of all statin medications taken by the participant. If the last statin is recorded as ongoing at study end date, the maximum statin end date will be set to the study end date.

- If the participant was on a statin on or after this statin assessment day (maximum statin end date \geq statin assessment date), the participant will be considered as discontinued statin = 'no.'
- If the participant was not on a statin on and after this statin assessment day (maximum statin end date $<$ statin assessment date), or they were a completer who did not have a Day 330 visit, the participant will be considered as discontinued statin = 'yes.'

All early termination participants will be considered to not be on a statin for this endpoint (the participant will be considered as discontinued statin = 'yes').

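### Randomized participants who never start treatment are classed as early terminators and scored as statin discontinuers; this falls mainly on the inclisiran arm and conflicts with the all-randomized analysis

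*Protocol*

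**What the plan says.** **The rule.** Protocol 8.1.1 covers participants who are randomized but never begin treatment: "Participants who are randomized and fail to start treatment, e.g. participants randomized in error, will be considered an early terminator". The reason for early termination then goes on the case report form.

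**What follows from it in the SAP.**
- SAP 2.5.1, on primary variable 2 (statin discontinuation): "All early termination participants will be considered to not be on a statin for this endpoint". The score is 'yes', with no exception for a recorded ongoing statin.
- SAP 2.1.1 fixes completer status by one form entry: "Completers are defined as a participant who has a Subject Status of" 'completed' on the Study Completion/Exit page. The same section links an early termination visit to leaving the study before Day 330.

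**Who can fail to start.** SAP 2.1.1: "For the usual care alone group the study treatment start date will be the randomization date". An inclisiran-arm participant who "does not take any study drug then treatment start date will be the randomization date". Table 2-1 of the SAP has a row for inclisiran-arm participants who "Never received inclisiran" and keeps them as planned Inclisiran First.

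**Text pointing the other way.**
- Protocol 12.1: "The Full Analysis Set (FAS) comprises all randomized participants".
- Protocol 9.1.1: those who discontinue study treatment "should NOT be considered withdrawn from the study UNLESS they withdraw their consent". Protocol 8 keeps them on the visit schedule.
- Both primary estimands (Protocol 2.1, SAP 1.2.1) ignore discontinuation of study treatment.

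**The concern.** A participant who takes one dose and stops is followed to Day 330. One who takes none is, on a literal reading of 8.1.1, an early terminator. Under the SAP start-date convention a usual-care participant cannot be in that position, so the trigger comes after randomization and depends on the arm. The trial is open-label, so a first dose can be missed after the assignment is known.

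Two analyses are exposed:
- **Statin non-inferiority.** An undosed participant who takes a statin throughout still counts as a discontinuer, which raises the inclisiran proportion artificially.
- **LDL-C.** If visits stop, the participant has no post-baseline value and adds nothing to the MMRM. The comparison then becomes inclisiran starters against everyone in usual care, which is not the treatment-policy effect that the estimand describes.

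**Working it through.** **1. Reproduce the design (Protocol 12.8.1).**

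Inputs: discontinuation proportion 0.20 in each arm, margin 0.15, one-sided alpha 0.0125, power 0.90; LDL-C difference 15, SD 40, two-sided alpha 0.025. In both cases z(0.9875) = 2.2414, z(0.90) = 1.2816, and (2.2414 + 1.2816)² = 12.41.

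- Variable 2: n per arm = 12.41 × (0.16 + 0.16) / 0.15² = 176.5, so 177; total 354, as stated.
- LDL-C: n per arm = 2 × 40² × 12.41 / 15² = 176.5, so 177; total 354, as stated.
- Inflation: 354 / 0.80 = 442.5, so 443, against about 444 stated.

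**2. Shift in the statin endpoint.**

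Let x be the share of the inclisiran arm that never starts. The documents give no value, so x is assumed. Suppose these participants would truly stop statins at the planned 0.20 but are all scored 'yes'. Then

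p(inclisiran) = 0.20(1 − x) + x = 0.20 + 0.80x,

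while usual care stays at 0.20. Each 1% adds 0.8 points to the difference, against a margin of 15 points.

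**3. Effect on power.**

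Power = Φ[(0.15 − shift) / SE − 2.2414], with unpooled SE. Worked case, x = 1% and 177 per arm:
- SE = √[(0.208 × 0.792 + 0.16) / 177] = 0.0428
- (0.15 − 0.008) / 0.0428 − 2.2414 = 1.07
- Power = 0.86

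Three settings are shown. The first is the planned evaluable number. The second is 200 per arm (222 less 10% statin intolerant), since in the FAS losses are scored rather than dropped. The third also scores the planned 10% loss as 'yes' in both arms, so the base proportion is 0.10 + 0.90 × 0.20 = 0.28 and each 1% of non-starters adds 0.72 points.

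| Non-starters (assumed) | 177 per arm | 200 per arm | 200 per arm, 10% loss scored 'yes' |
|---|---|---|---|
| 0% | 0.90 | 0.93 | 0.86 |
| 1% | 0.86 | 0.90 | 0.82 |
| 2% | 0.81 | 0.86 | 0.78 |
| 5% | 0.60 | 0.66 | 0.60 |

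If the same 5% were scored 'yes' in both arms, power at 177 per arm would still be 0.86. Most of the loss therefore comes from the imbalance between arms.

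**4. LDL-C.**

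Assume that non-starters respond like usual care. The treatment-policy difference is then 15(1 − x): 14.85 at 1% and 14.25 at 5%. If they have no post-baseline data, the estimate stays near 15. The overstatement is 15x: 0.15 points at 1% and 0.75 at 5%, against an SD of 40.

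**The case against.** The strongest reply is that 8.1.1 is a labelling sentence in a section on screening failures. It does not say that visits stop, and the glossary does not define an early terminator. Protocol 8 and 9.1.1 favour continued follow-up, the FAS keeps everyone randomized, and SAP Table 2-1 expects undosed inclisiran participants in the data.

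Much of this stands, and it rules out several stronger readings that a reader might infer:

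- **That non-starters are removed from the analysis.** They are not. They remain in the FAS and, unless statin intolerant, in the variable 2 denominator. LDL-C is missing only if no post-baseline sample is taken. A final visit soon after randomization would supply a value, but it would fall in the SAP's Day 90 window and leave Day 330 empty.
- **That the rule applies to the inclisiran arm alone.** 8.1.1 names no arm, its own example of randomization in error can occur in either, and Protocol 6.1 lists usual care under study treatment. The imbalance is inferred from the SAP start-date convention.
- **That many participants will be affected.** Table 8-1 puts randomization and the first dose at the same visit, so non-starters are probably few. The 5% row in the table is an illustration, not a forecast.
- **That false non-inferiority could result.** The scoring raises the inclisiran proportion, so it can only make non-inferiority harder to show.

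The reply does not dispose of the conflict. Protocol 8 and 9.1.1 speak of participants who discontinue treatment, and the glossary describes that as stopping treatment, so those who never began are not clearly covered. 8.1.1 is the only sentence that tells sites how to class them. Nor does the general missing-data rule explain the scoring: SAP 2.5.4 assumes discontinuation only where statin use cannot be ascertained, whereas SAP 2.5.1 imposes it on every early terminator.

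**Conclusion.** The concern holds in a limited form. Read literally, Protocol 8.1.1 and SAP 2.5.1 together turn a missed first dose into a statin discontinuation, mainly in the inclisiran arm, and may end LDL-C follow-up. That conflicts with the all-randomized FAS, the estimands and the follow-up rules.

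The size depends on a non-starter rate that the documents do not give. At 1%, about 2 of 222, power for non-inferiority falls by 3 to 4 points in each setting: 0.90 to 0.86, 0.93 to 0.90, or 0.86 to 0.82. The error is conservative for that test. The LDL-C bias favours inclisiran but is only about 0.15 points per 1%. The two effects fall on separate tests and do not offset each other.

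These figures assume that non-starters are recorded as non-completers, would otherwise have been followed, stop statins at the planned rate of 0.20 (0.28 in the third setting, where the planned loss counts as 'yes'), and respond on LDL-C like usual care. If nobody misses the first dose, nothing changes.

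**What to change.** **Protocol 8.1.1.** Replace the sentence with, for example: *Randomized participants in either arm who do not start study treatment remain in study follow-up to Day 330 and in the FAS as randomized, unless they withdraw consent or are lost to follow-up (see Section 9.1.1).* This should expressly include those randomized in error, and should say how a non-starter who attends to Day 330 is recorded on the Study Completion/Exit page.

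**SAP 2.5.1.** The protocol change alone leaves the scoring of early terminators in place. Score non-starters on recorded statin use from the eCRF, EHR or claims where available, and impute 'yes' only where statin status cannot be ascertained, in line with SAP 2.5.4. This part still helps if some participants' visits have already ended.

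**Reporting.** Give the number of non-starters by arm.

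**Cost.** One amended sentence and a site memo, standard visits for what are probably a few undosed participants, and minor programming.
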